### **First Study Visit**

The first study visit for subjects who pass the screening process will require a visit to the EPARC laboratory for approximately two hours. Subjects should attend fasted from 7.30PM the previous evening, though they are allowed to continue drinking water. Subjects should not have engaged in any significant exercise for 24 hours prior to the test.

Testing will begin between 7AM and 8AM at the EPARC laboratory in the Qualcomm Institute (i.e Atkinson Hall) on the UCSD campus. A free designated parking space will be provided and laboratory staff will escort the subject into the lab where the testing takes place. Participants will have their age, height, weight and gender recorded, and undergo a 15-minute assessment of (sitting) resting energy expenditure (EE) using indirect calorimetry (COSMED, Italy) following a standardized protocol in which the subject is asked to sit quietly while watching a nature or science documentary from Netflix on a (provided) tablet computer. The subject will be fitted

with a mask that captures (and analyzes) all of their expired air to calculate oxygen uptake (VO2), carbon dioxide production (VCO2), energy expenditure (EE), and substrate (carbohydrate and fat) utilization.

The subject will then be randomized to treatment sequences via a randomized block procedure, with block sizes randomly chosen in the set {2, 4, 6}. Subjects will be assigned 1:1 between an initial active stimulation, and initial sham stimulation as a control. This will be done in a double-blind manner, and whichever group a subject is randomized to on their first visit they will crossover to the other group on their second study appointment. So if a subject is initially randomized to what happens to be the active stimulation protocol, then on their second study visit that subject will crossover and receive the sham protocol, and vice versa.

The subject will then undergo 45 minutes of either vestibular nerve stimulation or sham stimulation, as described below. The subject will continue to sit quietly watching a science or nature documentary. During this 45-minute stimulation period the subject will have their EE measured during the middle 15 minutes.

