### **Specific Measure**

The Cosmed CPET, or portable K4B2, metabolic assessment unit will be used for all measurements of indirect calorimetry. Subjects are fitted with a pliable facemask that covers their nose and mouth, and allows for normal breathing. However, the facemask allows us to measure all of the air the subject inspires as well as the fractional composition of inspired and expired gases. EE and substrate utilization are derived from the VO2 and VCO2 measurements.

The primary endpoint of the study will be change in fat consumption from the baseline measurement, and the secondary endpoint will be the change in energy expenditure from the baseline.

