Similarly, in February 2016, Halo Neuroscience, a company based in San Francisco, released additional data on the safety of tES; on this occasion for a 2mA tDCS device used on 1010 subjects. They state that “there were zero reports of burn or seizure activity across all 1010 subjects, zero serious or unexpected adverse effects and zero withdrawals due to adverse events other than unpleasant sensation”. They conclude that their tES study showed “a favorable safety profile and [was] associated with a very low incidence of adverse events, with no unexpected or serious adverse events”.

Specific measures taken to reduce the incidence of skin irritation are the 27mm diameter of the electrodes, which are themselves hypo-allergenic, and the 50% duty cycle (i.e. half the time no current at all is being delivered), and the maximum current of 1.0mA. This means that the

---

 <https://halo-website-static-assets.s3.amazonaws.com/whitepapers/safety.pdf>

maximum phase current that can be delivered is only 500 $\mu$ C. In conclusion, there is not a significant risk of harm from using the device, and as such criteria d and g do not apply. Thus as the device does not meet the criteria of a SR device it is a NSR device.

Based upon the statistical power calculations, the aim is to enroll a total of 20 subjects. There will be no exclusion from the study on the basis of race, socioeconomic status, language spoken, or ethnicity.

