## 1.2 Analysis Plan and Sample Size Calculation

To account for potential period effects, a cross-over design will be used to assess the effect of VeNS on fat consumption. Subjects will be randomized to either the Sham VeNS sequence or VeNS Sham-sequence. To eliminate the effect of period and sequence effects, standard cross-over design analysis will be performed with an independent samples t-test of differences between the first and second measurement by sequence (Sham → VeNS or VeNS → Sham).

When  $n = 10$  subjects data have been collected, we will perform an interim analysis of the primary aim. Our only considerations will be whether to stop the study to reject the null hypothesis or to continue to full recruitment. As such, we will apply the Pocock alpha spending function to account for the effect of this interim look on the type I error of the study. This amounts to using a significance level of 0.0294 at both the interim analysis and the final analysis, in order to maintain an overall type I error rate of 0.05.

With a total sample size of  $n = 20$  subjects, we will have 80% power at the  $\alpha = 0.05$  significance level (adjusted for two analyses with the Pocock alpha spending function) to detect a medium effect size of  $d = 0.72$ . Assuming a moderate within-subject correlation of  $\rho = 0.50$  and a standard deviation of mean fat consumption over the 60 minute treatment period of  $\sigma = 5.44$ , this translates to a detectable difference in fat consumption of 3.9%.

[figure not shown]

Figure 1: Detectable effect sizes by total sample size (A), and detectable effect sizes in terms of fat consumption assuming certain within-subject correlations (B).

[figure not shown]

Figure 2: Pilot data of energy expenditure over a two hour period for  $n = 3$  subjects.

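### Is the efficacy-only interim look at 10 subjects a design error, because a stop there overstates the effect and halves the data?

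*Combined protocol and SAP*

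**What the plan says.** All of the interim plan is in the SAP, section 1.2. When 10 "subjects data have been collected, we will perform an interim analysis of the primary aim". The look can lead to one of two actions: "Our only considerations will be whether to stop the study to reject the null hypothesis or to continue to full recruitment". There is no futility rule. The level is given as "using a significance level of 0.0294 at both the interim analysis and the final analysis", chosen "in order to maintain an overall type I error rate of 0.05". With 20 subjects the section claims 80% power for d = 0.72 after that adjustment. With within-subject correlation 0.50 and SD 5.44 it translates this into a difference of 3.9%.

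Three other places bear on the point. The protocol, under Specific Measure, says that "the secondary endpoint will be the change in energy expenditure from the baseline"; no power and no interim rule are given for it. Under First Study Visit, "whichever group a subject is randomized to on their first visit they will crossover to the other group on their second study appointment", so every completer receives both conditions. The Risk Assessment in Appendix 1 concludes that "there is not a significant risk of harm from using the device".

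**The concern.** An efficacy look at half of a 20-subject trial is small, and only large observed effects can cross the boundary. At 8 degrees of freedom the boundary corresponds to an observed standardised effect of about 0.84, above the 0.72 the trial is designed to detect. Trials that stop are therefore selected for overestimates, and the SAP does not say how the effect would then be reported. Energy expenditure would be left with 10 subjects. The usual ethical reason for an efficacy stop, sparing later patients an inferior arm, is weak when everyone receives both conditions and the device is rated non-significant risk. A single test at n = 20 has the same maximum size, more power and no average bias. If the look were a mistake, a positive trial could report an effect about a third too large from 10 people, and a later study sized on that effect would be too small.

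**Working it through.** **Inputs.** From section 1.2: looks at n = 10 and n = 20, level 0.0294 at each, d = 0.72, correlation 0.50, SD 5.44, and a two-sample t-test of period differences by sequence. Assumed: two-sided tests, sequences balanced 5/5 and then 10/10, normal differences, no dropout.

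**1. Scale.** SD of the within-subject difference = 5.44 × √(2 × (1 − 0.50)) = 5.44. The detectable difference is 0.72 × 5.44 = 3.92, matching the stated 3.9.

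**2. The stated power.** Noncentral t with noncentrality d√n and n − 2 degrees of freedom. At n = 20 and level 0.0294 the noncentrality is 0.72 × √20 = 3.22, the critical value on 18 df is 2.366, and power is 0.796. Simulating both looks gives 0.81. The 80% claim is reproduced, with the cost of the look already in it.

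**3. Type I error.** Using 0.0294 at both looks gives 0.0500 with known variance and about 0.0515 with t-tests on 8 and 18 df. The excess is small.

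**4. Behaviour at the look.** The critical t on 8 df is 2.647, and 2.647/√10 = 0.837. Simulated results (1,000,000 trials or more per row; mean n = 20 − 10 × stop probability):

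| True d | Stops at n = 10 | Mean estimate given a stop | Power with look | Power, one test at n = 20, 0.05 | Mean n with look |
|---|---|---|---|---|---|
| 0.50 | 21% | 0.87 (+74%) | 0.50 | 0.56 | 17.9 |
| 0.72 | 41% | 0.97 (+35%) | 0.81 | 0.86 | 15.9 |
| 1.00 | 69% | 1.13 (+13%) | 0.979 | 0.988 | 13.1 |

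The concern's arithmetic is therefore sound.

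**5. Like with like on bias, at d = 0.72.** The +35% is conditional on an early stop, whereas the zero bias of a single test is an average over all its runs.

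| Comparison | With look | One test at n = 20 |
|---|---|---|
| All runs | 0.772 (+7%) | 0.720 (0%) |
| Significant results only | 0.851 (+18%) | 0.774 (+7.5%) |

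A gap remains on either basis, but it is much smaller than 35% against nothing. The unadjusted 95% interval covers 0.937 given a stop and 0.950 overall, which is not a material problem.

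**6. Like with like on power.** The single test at n = 20 uses 20 − 15.9 = 4.1 more subjects on average. A fixed test with 16 subjects at 0.05, close to the sequential design's mean size, has power 0.76 at d = 0.72, against 0.81. At d = 1.0 the look saves 20 − 13.1 = 6.9 subjects for 0.988 − 0.979 = 0.009 of power.

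**7. The stricter-boundary alternative.** O'Brien-Fleming-type levels of 0.0052 and 0.0469 cut stops at d = 0.72 from 41% to 15%, reduce average bias to +3.9% and raise power to 0.856. They also raise the overstatement given a stop from +35% to +51% and the mean n to 18.5. If conditional overstatement is the fault, this makes it worse.

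**The case for a change.** The strongest contrary case is that the look buys little in this trial. No subject is held on an inferior arm, the maximum is only 20 subjects, the saving is about 4 of them at d = 0.72 and about 0.3 if there is no effect, and the SAP gives no reason for wanting to stop early. Against that stand a loss of about 5 points of power and a two-in-five chance that the main result rests on 10 people. A follow-on crossover of 12 subjects, sized on an effect of 0.97, would have power of only about 0.61 if d is 0.72. For energy expenditure, if its effect were also 0.72, power would fall from 0.86 to 0.52.

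Much of this stands as an argument for choosing a fixed design, and many statisticians would choose one. It does not show that the chosen design fails. Stopping at 10 spares up to 10 people two fasted morning visits, the mask, and the skin irritation, nausea and occasional vomiting that the protocol lists as risks; non-significant risk is not zero burden. The stated aim in SAP section 1.1 is whether stimulation changes fat consumption, and no precision target is set. The documents mention no follow-on trial. The secondary-endpoint figures rest on an effect size the documents do not give, for an endpoint on which the SAP claims no power.

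One part stands without qualification: the SAP does not say how the effect estimate, or energy expenditure, is reported after a stop. A sentence on each would help, but no stated method or figure is wrong for lack of it.

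**Conclusion.** The concern does not hold as an error in the plan. The look is pre-specified with a single stated action, its level is adjusted, type I error is about 0.05 (0.0515 with t-tests), and the promised 80% power is delivered net of the adjustment (0.796 at the final test alone, 0.81 over both looks). The overstatement after a stop is real, about +35% at d = 0.72 and larger for weaker effects. It is a known property of efficacy stopping, amounts to +7% over all runs, and comes with a mean saving of about 4 subjects at d = 0.72 and 7 at d = 1.0. Dropping the look or tightening its boundary trades one property for another, and reasonable statisticians differ on it. What remains is missing detail on reporting after a stop.

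The figures assume two-sided tests, balanced sequences at both looks, normal differences and no dropout. Under the normal approximation a stop at d = 0.72 is more likely (54%), the overstatement given a stop is similar (+32%), and power is 0.87 with the look against 0.90 without. The conclusion is the same.

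### The Pocock alpha spending function named in the SAP does not give 0.0294 at both looks, and the 0.05 overall error is only approximate for the small-sample t-test (a minor point)

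*Combined protocol and SAP*

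**What the plan says.** All of the decision rule is in SAP section 1.2, Analysis Plan and Sample Size Calculation.

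- **Timing.** The interim look comes at this point: "When $n = 10$ subjects data have been collected". The planned total is 20 subjects. The interim can stop the trial only to reject the null; there is no futility stop.
- **Method named.** "we will apply the Pocock alpha spending function to account for the effect of this interim look on the type I error of the study". The power sentence in the same section names the spending function again.
- **Threshold.** "This amounts to using a significance level of 0.0294 at both the interim analysis and the final analysis", with the stated purpose "in order to maintain an overall type I error rate of 0.05".
- **Test.** "an independent samples t-test of differences between the first and second measurement by sequence".

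The section does not say whether the t-test pools the variances or is a Welch test. It gives no degrees of freedom, does not state sidedness, and makes no small-sample adjustment of the threshold.

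**The concern.** Two features of the threshold need checking.

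First, the Pocock spending function and the Pocock constant boundary are related but different procedures. The spending function fixes how much error is used by a given information fraction, and its nominal levels generally differ between looks. The constant boundary uses the same level at each look. The SAP names the first and prints the number that belongs to the second.

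Second, 0.0294 comes from normal theory with known variance. The plan applies it to t-tests on very small groups, where the joint behaviour of the two test statistics is different.

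This is the only efficacy decision rule in the trial, and the SAP attaches a specific error guarantee to it. An analyst who implements the named method would use other thresholds than one who implements the printed number. An interim p-value between 0.0294 and 0.0310, or a final p-value between 0.0277 and 0.0294, would be judged differently.

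**Working it through.** **Inputs.** From SAP section 1.2: overall error 0.05, nominal level 0.0294 at both looks, interim at 10 subjects, final at 20, independent-samples t-test by sequence, d = 0.72. From the protocol, First Study Visit: 1:1 allocation to sequence in random blocks of 2, 4 or 6. Assumed: two-sided testing (the reading under which 0.0294 arises), normal data, and complete data split 5 + 5 then 10 + 10 unless stated otherwise.

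**Step 1. Reproduce 0.0294.** With information fraction 10/20 = 0.5, the two z statistics have correlation √0.5 = 0.707. Solving P(|Z1| < c and |Z2| < c) = 0.95 gives c = 2.1783, and 2 × (1 − Φ(2.1783)) = 0.02939, which rounds to 0.0294. Using 0.0294 at both looks gives an overall error of 0.0500. The printed constant is therefore right for two equally spaced z-tests.

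**Step 2. Apply the named method.** The Pocock-type spending function is α(t) = α × ln(1 + (e − 1)t).

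- Interim: 0.05 × ln(1 + 1.718 × 0.5) = 0.05 × ln(1.859) = 0.05 × 0.620 = 0.0310 (boundary 2.157).
- Final: the boundary that brings the total to 0.05 is 2.201, a nominal level of 0.0277.

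One-sided readings do not rescue the match. At one-sided 0.05 the spending function gives 0.0310 and 0.0297, and the constant boundary is 0.0304.

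**Step 3. Apply 0.0294 to the t-test.** A pooled-variance test has 5 + 5 − 2 = 8 df at the interim and 10 + 10 − 2 = 18 df at the final. Overall error was simulated under the null.

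| Test and interim split | Levels (interim / final) | Overall type I error |
|---|---|---|
| Pooled, 5/5 | 0.0294 / 0.0294 | 0.0513 to 0.0515 (separate runs of 4 to 60 million trials) |
| Pooled, 4/6 | 0.0294 / 0.0294 | 0.0518 |
| Pooled, 7/3 | 0.0294 / 0.0294 | 0.0526 |
| Pooled, 5/5 | 0.0310 / 0.0277 | 0.0514 |
| Pooled, 5/5 | 0.0285 / 0.0285 | 0.0500 |
| Pooled, 5/5 | 0.0310 / 0.0261 | about 0.050 |
| Welch, 5/5 | 0.0294 / 0.0294 | 0.0468 to 0.0470 |

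The pooled excess arises because the two looks overlap less. Each look alone rejects at 0.0294, so overall error is 2 × 0.0294 minus the probability that both reject. For z-tests that probability is 0.0588 − 0.0500 = 0.0088; for the pooled t-tests it is 0.0588 − 0.0515 = 0.0073. The fourth row shows that the naming mismatch is not the cause: the spending-function levels have almost the same excess.

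On the split: if the first ten randomised are also the first ten analysed, the even block sizes allow at worst 6/4. A 7/3 split would need dropouts or completion out of order.

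**Step 4. Power at d = 0.72, pooled test.** At 0.0294, power is 79.6% at the final look alone and about 81.2% to 81.3% over both looks. At 0.0285, two-look power is about 80.8% to 80.9%.

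**Step 5. How often the choice matters.** The 0.0294 pair and the 0.0310 / 0.0277 pair lead to a different trial decision in about 0.3% of trials under the null and about 0.75% at d = 0.72.

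**The case against.** The strongest reply is that 0.0294 is a recognised and correct constant, that the SAP prints one number for both looks, and that an analyst following the text would use it. On this view the only fault is a loose label. The first two statements stand. A reader might infer that the sponsor miscalculated the threshold, or that the SAP contains two competing pairs of thresholds. The documents support neither: Step 1 reproduces 0.0294, and 0.0310 and 0.0277 appear nowhere in the SAP. They follow only from working through the method it names. The SAP nevertheless says that the named method amounts to the printed number, and that is not so.

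The second reply concerns the error rate. The excess over 0.05 is about 0.0015, it depends on pooled variances, and a Welch test falls below 0.05. Normality cannot be relied on to the fourth decimal with five subjects per sequence. All of this stands. It limits the size of the point and rules out an unconditional claim of inflation, but it also shows that the stated guarantee depends on a choice the SAP leaves open.

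Third, a replacement constant such as 0.0285 carries conditions of its own: pooled variances, normal data and a 5/5 interim split. That is fair, and those conditions should be written beside it.

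**Conclusion.** The statement is wrong as written, and the effect is minor. The Pocock-type spending function at 10 of 20 subjects gives about 0.0310 then 0.0277 (two-sided, normal theory). The 0.0294 pair is the constant Pocock boundary for z-tests. This is a mismatch between the named method and the number, and it does not depend on which t-test is used.

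For the planned t-test the 0.05 guarantee is approximate: about 0.0514 to 0.0515 with pooled variances and about 0.047 with Welch, both for normal data split 5 + 5 then 10 + 10. A reader might conclude that the trial simply exceeds its 5% error rate. The documents do not support that, because they specify neither pooled variances nor degrees of freedom, and the direction of the departure turns on that choice. The stated 80% power is not affected.

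**What to change.** State one rule and the test it is calibrated to. Either of these would do:

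1. **Constant boundary.** Specify a two-sided pooled-variance t-test with a constant Pocock-type nominal level of 0.0285 at 10 and at 20 completed subjects. Say that this gives an overall type I error of about 0.05 under normality with a 5/5 interim split. Delete the references to an alpha spending function, including the one in the power sentence.
2. **Spending function.** Keep it, give its formula, drop 0.0294, and compute both thresholds for the stated t-test at the numbers per sequence actually available. For a pooled test at 5/5 and 10/10 these are about 0.0310 and 0.0261.

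If the sponsor prefers a Welch test, the SAP should say so. The 0.0294 level is then already conservative for equal splits and 0.0285 is not needed; only the method name has to change.

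The cost is one or two sentences and no extra subjects. Under option 1, two-look power at d = 0.72 falls by about 0.4 percentage points, from about 81.3% to 80.9%, and stays above the stated 80%.

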## **STUDY PROTOCOL**

### **Study Design**

- Crossover design
- Double-blind
- Randomized
- Primary endpoint classification: Change in fat consumption from baseline
- Secondary endpoint classification: Change in energy expenditure from baseline

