After the 45-minute stimulation period ends the subject will remain in the EPARC facility for one more hour. They will continue to sit quietly and watch a documentary. During this 1-hour post-stimulation period the subject will undergo two more 15-minute measurements of their EE. The first 15-minute measurement will take place during the first 15 minutes of this one-hour post-stimulation period, and the second 15-minute measurement will take place during the final 15 minutes of the one-hour post-stimulation period.

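### The 3.9% detectable difference is not shown for the primary endpoint: SAP 1.2 derives it from the SD of a 60-minute mean, while the protocol's endpoint is change from a 15-minute baseline

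*Combined protocol and SAP*

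**What the plan says.** The protocol defines the endpoint twice. Under Study Design: "Primary endpoint classification: Change in fat consumption from baseline". Under Specific Measure: "The primary endpoint of the study will be change in fat consumption from the baseline measurement".

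Each visit has four 15-minute windows. The first is the baseline, before stimulation. For the second, First Study Visit says: "During this 45-minute stimulation period the subject will have their EE measured during the middle 15 minutes". For the other two: "During this 1-hour post-stimulation period the subject will undergo two more 15-minute measurements of their EE". These fall at the start and the end of that hour. Second Study Visit repeats the schedule. Fat use comes from the same gas readings as energy expenditure ("EE and substrate utilization are derived from the" oxygen and carbon dioxide measurements), so each window can yield a fat value.

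SAP section 1.2 plans an "independent samples t-test of differences between the first and second measurement by sequence". It assumes a within-subject correlation of 0.50 and σ = 5.44, described as the "standard deviation of mean fat consumption over the 60 minute treatment period", and concludes that "this translates to a detectable difference in fat consumption of 3.9" percent. Sections 1.1 and 1.2 do not mention baseline. Section 1.1 speaks of a change in fat consumption as the general aim, without naming a reference point.

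**The concern.** The two documents appear to describe different variables. The protocol subtracts a 15-minute baseline at each visit. The SAP's SD is worded as that of a mean with nothing subtracted, taken over a period of treatment that the visit schedule does not contain. No section says which of the three later windows, or which mean of them, enters the t-test.

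Subtracting baseline has two opposing effects. It adds the noise of two baseline windows per subject, one per visit. It also removes whatever day-to-day variation the baseline shares with the later reading on the same day. Which effect is larger decides whether 20 subjects can detect 3.9, more than 3.9, or less. If 3.9 is quoted when a null result is interpreted, the reader needs to know that it belongs to the variable tested. The variable also has to be fixed before the look at 10 subjects, because that look can stop the trial.

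**Working it through.** **Inputs from SAP 1.2:** d = 0.72, σ = 5.44, ρ = 0.50, 20 subjects, significance level 0.0294 at each of two looks (10 and 20 subjects). **From First Study Visit:** 1:1 allocation, so 10 per sequence at the end. **Assumed:** two-sided tests (the SAP does not say) and no dropout.

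**1. The plan's own figure.** With one value per visit, the SD of the within-subject difference is 5.44 × √(2 × (1 − 0.50)) = 5.44. Then 0.72 × 5.44 = 3.92, the stated 3.9. The two-sample t-test by sequence has 79.6% power at the final look alone and 81% over both looks (simulated). The stated 80% reproduces.

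**2. What the formula does not settle.** It takes one value per visit. That value could be an unsubtracted mean or a change, so the formula alone does not show which was meant. The SAP's description of 5.44 points to an unsubtracted mean.

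**3. If 5.44 and 0.50 describe unsubtracted values and the change is tested.** Take one later window with the same SD as baseline, and the same correlation for every pair of readings from different visits. Let r be the correlation between baseline and the later window at one visit. The documents give no r.

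- Variance of (visit-1 change − visit-2 change) = 4 × 5.44² × (1 − r). The between-visit correlation cancels.
- Detectable difference = 0.72 × the square root of that variance.
- At r = 0.50: √(4 × 29.59 × 0.50) = 7.69, and 0.72 × 7.69 = 5.5.
- The result equals 3.92 when 4(1 − r) = 1, that is, r = 0.75.

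Power for 3.92 over both looks, by simulation. The covariate analysis regresses the between-visit difference in the later value on sequence and on the between-visit difference in baseline.

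| r | SD of difference in changes | Detectable difference, change score | Power, unsubtracted value | Power, change score | Power, baseline as covariate |
|---|---|---|---|---|---|
| 0.50 | 7.69 | 5.5 | 81% | 51% | 78–79% |
| 0.625 | 6.66 | 4.8 | 81% | 64% | 81% |
| 0.75 | 5.44 | 3.9 | 81% | 81% | 89% |
| 0.875 | 3.85 | 2.8 | 81% | 98% | 99% |
| 0.95 | 2.43 | 1.8 | 81% | nearly 100% | nearly 100% |

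At r = 0.50 a baseline taken the same morning says no more about the later reading than one from the other visit, so baseline carries no information for the comparison. Overall type I error was 5.1–5.3% for all three analyses.

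**4. If the later value averages two or three windows** and 5.44 is the SD of that average, the single-window baseline is noisier than the average. Let f be the share of the within-subject variance that is common to one day (for one window, r = 0.50 + 0.50f). Over f from 0 to 0.9, change-score power for 3.92 runs from 37% to nearly 100% with two windows and from 29% to 99.5% with three. The low ends need a baseline SD above 5.44, which the documents do not give. The covariate analysis stayed at about 78% or more in every setting.

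**5. If 5.44 is instead the SD of the change,** 3.9 holds when the two visits' changes correlate 0.50. With no correlation, the SD of their difference is 5.44 × √2 = 7.69, the detectable difference is 5.5 and power for 3.9 is 51%. At 0.75 they are 2.8 and 98%.

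**The case against.** The strongest reply is that the SAP is brief rather than in conflict with the protocol. Its test compares one value per visit, and that value could be the protocol's change score; its formula fits a change as well as an unsubtracted mean. On that reading 5.44 and 0.50 may already describe changes, and nothing is wrong beyond loose wording. The reference to 60 minutes may describe the source of the SD, the post-stimulation hour, or the four 15-minute windows together (4 × 15 = 60). The caption of Figure 1B says that detectable differences were plotted for several within-subject correlations; the figure is not in the text available here.

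Much of this stands. The SAP cannot be said to have chosen the unsubtracted value, and 5.44 cannot be said to be wrong. The standardised claim (20 subjects, d = 0.72, about 80% power) is untouched.

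A reader might infer from the 51% that the trial is underpowered. The documents do not support that: r is an assumption, and above 0.75 the trial with one later window has more power than stated. Windows within one morning may well correlate more closely than visits at least two weeks apart.

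The reply does not remove the conflict in the text. The SD is described as that of a mean over a period the schedule lacks, and none of the possible 60-minute readings is stated or is a change from baseline. A plot over correlations would not by itself say which variable they belong to.

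**Conclusion.** The point holds in a limited form. SAP 1.2 does not show that d = 0.72 corresponds to 3.9% for change from baseline. The sample size arithmetic is correct, and power at d = 0.72 is about 80% for any single value per visit.

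The size of the gap cannot be fixed from the documents. If 5.44 and 0.50 describe unsubtracted values and one later window is used, the detectable difference for a change score runs from 5.5 to 1.8, and power for 3.9 from 51% to nearly 100%, as r goes from 0.50 to 0.95. The stated 3.9 is met at r = 0.75. These figures assume equal SDs for baseline and the later window, equal cross-visit correlations, two-sided tests and no dropout. They bound what the omission could mean and do not establish lost power. The point should be fixed before the look at 10 subjects.

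**What to change.** Before the look at 10 subjects:

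1. State the same single value per visit in Study Design, Specific Measure and SAP 1.2, naming the window or the mean of windows. Use it at both looks.
2. Say what 5.44 and 0.50 describe (variable, averaging period, unit, source). If that is not the analysed value, give its SD and correlation and restate the 3.9%.
3. Reconcile the SAP's 60 minutes of treatment with the 45 minutes in the visit, stimulation and risk management sections, and with the measured windows.
4. Use baseline as a covariate in place of an unadjusted value or a simple change score: regress the visit-1 minus visit-2 post-baseline value on sequence and on the visit-1 minus visit-2 baseline. The sequence coefficient is the same whether the response is the later value or its change from baseline, so the protocol's endpoint can stay as worded. The treatment effect is half that coefficient in size, as in the planned t-test.

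If 5.44 and 0.50 describe unsubtracted values, step 4 keeps power for 3.9 at about 78% or more over the range examined and was never below the change score. It costs one degree of freedom: about 78% instead of 81% if baseline carries no information. The whole change needs a few sentences, a check of where 5.44 and 0.50 came from, and no new visits or data.
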